4.1.2 Day 1 (\pm 3 days) of Each Cycle

Day 1 of each cycle occurs on infusion day. The following procedures will be performed prior to ADCT-402 infusion (unless otherwise indicated) at each cycle.

- Serum or urine β -HCG pregnancy test (women of child-bearing potential, Cycle 1 only) required if the screening pregnancy test was obtained >7 days prior to Day 1.
- Physical examination, including whole body skin assessment, unless an assessment was performed within 3 days prior to Day 1.

ADCT-402-102 Protocol Amendment 3

• Vital signs: On Day 1 of Cycles 1 and 2, vital signs are to be measured before the start of ADCT-402 infusion, every 30 minutes during the infusion, at the end of infusion, and at 1, 3, and 6 hours after the end of infusion. If no clinically significant changes occur during the Cycles 1 and 2, vital sign measurements are to be obtained prior to the start of and at the end of ADCT-402 infusion for all subsequent cycles. If clinically significant changes in vital signs are observed at Cycle 1 and/or 2 infusion, that patient will be required to have vital signs measured before the start of the ADCT-402 infusion, every 30 minutes during the infusion, at the end of infusion, and at 1, 3, and 6 hours after the end of the ADCT-402 infusion for all subsequent cycles.

- Weight, unless an assessment was performed within 3 days prior to Day 1.
- ECOG performance status.
- Hematology, coagulation panel, and biochemistry parameters, will be measured prior to dosing unless the last sample was collected:
 - o <24 hours before the start of ADCT-402 infusion on Day 1 of Cycle 1, or
 - <72 hours before the start of ADCT-402 infusion on Day 1 of Cycle 2 and subsequent cycles.
 

- Sample collection for
 - o Additional renal function studies
 - Urinalvsis

Prior to dosing unless the last sample was collected:

- o <24 hours before the start of ADCT-402 infusion on Day 1 of Cycle 1, or
- <
- 12-lead ECG (Cycles 1 and 2) before the start of the ADCT-402 infusion, within 30 minutes of the end of infusion, and 3 hours (± 30 minutes) and 24 (± 2.4) hours after the end of infusion (Table 5 and Table 7 in Appendix 12.1). For Cycle 3 and subsequent cycles, a 12-lead ECG is to be performed before the start of ADCT-402 infusion.
- Sample collection for central laboratory analysis of ADA (all cycles).
- Sample collection (Cycles 1 and 2) for central laboratory analysis of PK parameters before the start of the ADCT-402 infusion, at the end of the infusion, and at 1, 3, and 6 hours after the end of the ADCT-402 infusion. For Cycle 3 and subsequent cycles, samples will be collected before the start of the ADCT-402 infusion and at the end of the infusion.
- Whole blood sample collection for central laboratory analysis of peripheral WBC populations and evaluation of CD19 and other CD markers (e.g., CD20, CD21, CD22) before the start of, and 3 hours after, ADCT-402 infusion on Day 1 (Cycles 1 and 2).

ADCT-402-102 Protocol Amendment 3

• MNC samples:

- Urine sample collection for central laboratory assessment of additional renal function studies.
- Collection of AE information.
- Collection of concomitant medication information.
- Premedication administration, if applicable (Section 5.2).
- ADCT-402 administration.

4.1.2.1 Bone Marrow Sample

Within 6 days prior to Day 1 of Cycle 3, a bone marrow sample (aspirate or biopsy if aspirate unattainable) will be obtained for assessment of response to treatment and determination of MRD (via flow cytometry) by an approved clinical laboratory. Results must be available to the Investigator before the next dose of study drug is administered.

A bone marrow sample will then be obtained within 6 days prior to the Day 1 visit of Cycle 5 and at each subsequent cycle until CR or CRi (Section 6.1) is achieved or until disease progression. Once CR/CRi is achieved, sampling will be repeated at least every 3 cycles, or as clinically indicated.

A bone marrow sample will also be collected at the EOT visit (Section 4.1.8) for those patients who have not demonstrated disease progression and if their most recent sample was obtained more than $12 (\pm 1)$ weeks prior to the EOT visit.

Bone marrow aspirate sample collection with subsequent MNC isolation should follow the same collection schedule as above. Mononuclear cells from BMA will be used for retrospective central laboratory evaluation of CD19 and other CD markers (e.g., CD20, CD21, CD22).

ADCT-402-102 Protocol Amendment 3

Samples obtained during treatment and at the EOT visit are to be saved for biobanking (see Laboratory Manual). Additionally, when available, results from other analyses conducted as part of the institution's standard of care will also be collected.

4.1.3 Day 2 (Cycles 1 and 2)

The following procedures will be performed 24 hours ($\pm 10\%$) after the end of the ADCT-402 infusion:

- 12-lead ECG.
- Vital signs.
- Sample collection for central laboratory analysis of PK parameters.
- Collection of AE information.
- Collection of concomitant medication information.

4.1.4 Day 3 (Cycles 1 and 2)

The following procedures will be performed 48 hours ($\pm 10\%$) after the end of infusion:

- Vital signs.
- Sample collection for central laboratory analysis of PK parameters.
- Collection of AE information.
- Collection of concomitant medication information.

4.1.5 Day 5 (Cycles 1 and 2)

The following procedures will be performed 96 hours (± 1 day) after the end of infusion:

- Sample collection for central laboratory analysis of PK parameters.
- Vital signs.
- Collection of AE information.
- Collection of concomitant medication information.

4.1.6 Day 8 (\pm 2 days) of Each Cycle

The following procedures will be performed at this visit:

- Physical examination including whole body skin assessment (Cycles 1 and 2).
- Weight (Cycles 1 and 2).
- Vital signs.
- Hematology and biochemistry parameters.
- Urinalysis.
- Urine sample collection for central laboratory assessment of additional renal function studies.
- Sample collection for central laboratory analysis of PK parameters (Cycles 1 and 2).

ADCT-402-102 Protocol Amendment 3

- Collection of AE information.
- Collection of concomitant medication information.

4.1.7 Day 15 (\pm 2 days) of Cycles 1 and 2

The Day 15 visit will be conducted during Cycles 1 and 2 only; the following procedures will be performed at this visit:

- Physical examination, including whole body skin assessment.
- Weight.
- Vital signs.
- Hematology and biochemistry parameters.
- Urinalysis.
- Urine sample collection for central laboratory assessment of additional renal function studies.
- Sample collection for central laboratory analysis of PK.
- Collection of AE information.
- Collection of concomitant medication information

4.1.8 End of Treatment Visit

The following procedures will be performed within 30 days (+ 7 days) after study treatment discontinuation:

- Serum or urine pregnancy test.
- Physical examination including whole body skin assessment.
- Weight and vital signs.
- ECOG performance status.
- Hematology, coagulation panel, and biochemistry parameters.
- Urinalysis and sample collection for assessment of additional renal function studies.
- 12-lead ECG.
- Sample collection for central laboratory assessment of PK and ADA.
- Whole blood sample collection for central laboratory analysis of peripheral WBC populations and evaluation of CD19 and other CD markers (e.g., CD20, CD21, CD22).
- MNC) samples:
 - Whole blood (WB) sample collection with subsequent MNC isolation for retrospective central laboratory evaluation of CD19 and other CD markers (e.g., CD20, CD21, CD22).

ADCT-402-102 Protocol Amendment 3

- Collection of AE information.
- Collection of concomitant medication information.
- Bone marrow sample for disease assessment (see Section 4.1.2.1).

4.1.9 12-week Follow-up Visit

Each patient will have a sample taken for assessment of PK and ADA at 12 (± 1) weeks after their last dose of ADCT-402.

Blood Sample Collection and Adverse Event Monitoring During Long-Term Follow-up

For all patients, a PK and ADA blood sample collection will be performed 12 weeks (± 1 week) following the last dose of ADCT-402.

For all patients, collection of AEs and SAEs will continue for up to 84 days (12 weeks) after the last dose of study drug or initiation of new anti-cancer treatment (see Section 6.3.3.2).

4.1.10 Long-term Follow-up

Patients who discontinue treatment for any reason other than disease progression will continue to be followed by telephone contact approximately every 12 weeks from the last disease assessment until disease progression, or initiation of new anti-cancer treatment.

After documentation of disease progression or start of new treatment, patients will be followed (by telephone contact or chart review) approximately every 12 weeks for up to 12 months after the last dose of study drug to collect survival information.

4.2 Withdrawal of Patients from the Study

The duration of the study participation for each patient is defined as the time from the date of signed written informed consent through the completion of the follow-up period or withdrawal of consent.

4.2.1 Reasons for Withdrawal/Discontinuation

Patients may withdraw from the study at any time and for any reason, without prejudice to their future medical care, by the Investigator or others at the study site.

A patient may be withdrawn from treatment with ADCT-402 for any of the following reasons:

- Disease progression.
- AE

ADCT-402-102 Protocol Amendment 3

- Withdrawal of consent.
- Major protocol deviation.
- Required treatment delay of >21 days (except in case of potential patient benefit, which must be approved by the Sponsor).
- Non-compliance, including lost to follow-up.
- Pregnancy.
- Other (e.g., development of contraindications).
- The Investigator determines that it is in the best interest of the patient to discontinue the patient's participation in the study.
- Discontinuation of the study by the Sponsor.
- Death.

Patients who experience the following significant toxicities will be immediately and permanently withdrawn from treatment with ADCT-402:

- Any patient who experiences a Grade 3 or higher hypersensitivity reaction (Appendix 12.2), regardless of premedication, during any cycle of treatment
- Any patient who experiences a protocol-defined DLT beyond Cycle 1 (except in the case of potential patient benefit, which must be approved by the Sponsor).
- Any patient who experiences a recurrent Grade 3 or 4 toxicity, excluding hematological toxicity.
- Any patient who requires a dosing delay >21 consecutive days from the planned Day 1 dosing at any time during treatment (except in case of potential patient benefit, which must be approved by the Sponsor).

4.2.2 Handling of Withdrawals

The Investigator will confer with the Sponsor if a patient experiences a serious or intolerable AE. If a patient discontinues from the study because of an AE, the patient will be followed to satisfactory resolution, until the Investigator deems the event to be chronic or not clinically significant, or until the patient is considered to be stable (Section 6.3.3.6).

ADCT-402-102 Protocol Amendment 3

For each patient who is withdrawn from treatment with ADCT-402 and withdraws from the study, the Investigator will record the reason(s) for discontinuation on the relevant page of the eCRF. Whenever possible, each patient who discontinues study treatment will undergo an EOT visit and all EOT assessments (Section 4.1.8). Patients who fail to return for final assessments are to be contacted by the investigative site. Following a minimum of 2 documented unsuccessful telephone calls, the investigative site will send a registered letter to the patient in a final attempt to ensure protocol compliance.

Note: Once withdrawn from the study, for any reason, patients are not permitted to be re-enrolled into the study.

4.2.3 Patient Replacements

Any patient in Part 1 who discontinues before completion of the first treatment cycle, for any reason other than a DLT, is to be replaced.

ADC Therapeutics ADCT-402
ADCT-402-102 Protocol Amendment 3

5 Study Treatments

5.1 Method of Assigning Patients to Treatment

In Part 1 (dose-escalation), patients will receive an IV infusion of ADCT-402, according to their assigned schedule. The first patient receiving the first dose of ADCT-402 in the study must be observed for 7 days for occurrence of AEs prior to treating a second patient. Patients will be entered sequentially to each dose level. The dose-escalation procedure is described in Section 3.2. If the highest allowed dose (600 μ g/kg) is reached and the MTD is not identified, no further dose-escalation will be allowed, pending a safety analysis and accordingly, an amendment to the protocol

In Part 2 (expansion), all patients will be assigned to the dose level of ADCT-402 identified in Part 1 by the DESC. Once the recommended Part 2 dose is determined, patients receiving lower dose levels of ADCT-402 may be offered continued treatment at the recommended dose.

5.2 Prophylactic Treatments for Hypersensitivity

If 1 patient experiences a Grade 2 or higher infusion-related hypersensitivity reaction (Appendix 12.2) at any time during Part 1 (dose-escalation), all subsequent patients must receive prophylactic treatment, as described below or as per the institution's standard of care, to reduce the risk of hypersensitivity reactions.

- On Day 1 of each cycle, patients will be instructed to take 20 mg orally of dexamethasone, at 12 and 6 hours before the start of ADCT-402 infusion. When necessary, 12 and 6 hours before the first infusion may be defined as "immediately before sleeping" and "immediately after waking up".
- On Day 1 of each cycle, patients will be given 50 mg IV of diphenhydramine hydrochloride at 30 minutes before the start of ADCT-402 infusion.
- On Day 1 of each cycle, patients will be given 50 mg of ranitidine (or equivalent) IV at 30 minutes before the start of ADCT-402 infusion.
- For 2 days following administration of ADCT-402 on Day 1, all patients are to take dexamethasone 4 mg orally, twice per day.

Other medications for prophylaxis and treatment of hypersensitivity or infusion reactions may be administered, according to standard treatment center protocols. Medications for the treatment of severe hypersensitivity reactions, including anaphylaxis, should be available for immediate use.

If a patient experiences a Grade 1 or 2 hypersensitivity reaction, the following medications (or equivalent) should be administered for 48 hours after ADCT-402 infusion:

- Ranitidine 150 mg orally, 2 times per day.
- Diphenhydramine hydrochloride 50 mg orally, 3 times per day.

ADCT-402-102 Protocol Amendment 3

Any patient who experiences a Grade 3 or higher hypersensitivity reaction (Appendix 12.2) should be withdrawn from treatment with ADCT-402 and immediately treated according to institutional standard of care and determined by the treating Investigator. These patients must be carefully observed after the treatment. Additional therapy, as per the institution's standard of care, should also be followed.

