The number of dose levels will depend on the emergent toxicity profile of ADCT-402 and will be decided by the DESC (Section 6.3.2); PK, and PD evaluations may also inform decision making.

Every 3 Week (Q3W) Administration

Patients will be given ADCT-402 on Day 1 of each 3-week treatment cycle.

Weekly (QW) Administration

Patients will be given ADCT-402 QW on Days 1, 8 and 15 of each 3-week (21-day) treatment cycle.

The first dose level for the QW dosing will be based on the safety and tolerability of patients who have been treated on the every 3-week (Q3W) schedule. The first 3 patients will be given a cumulative dose each cycle that is comparable to (but not higher than) the highest dose tested at the Q3W dose schedule at which 3 patients completed the DLT observation period without a DLT. For example, if the highest Q3W dose tested at which 3 patients did not experience a DLT was cohort 150 μ g/kg, the first cohort to receive QW dosing will receive 50 μ g/kg each week for 3 weeks.

A patient will maintain the same treatment schedule throughout the duration of the trial.

ADCT-402-102 Protocol Amendment 3

Weekly dosing will be implemented at the discretion of the DESC (and in accordance with local ethics committee approvals). Once a patient achieves CR/CRi, frequency or dose may be adjusted by the DESC based on emerging safety, efficacy and PK profile.

The trial will be continuously monitored for emerging safety, efficacy and/or PK profile and the DESC will determine if it is appropriate to maintain a QW schedule, revert to a Q3W schedule, or test other dosing regimens.

During Part 1, the DESC may expand enrollment at doses below the current dose level as part of the dose-escalation process. Additional patients may only be added at a lower dose level provided there is at least 1 patient who has achieved a PR (Section 6.1) or better. No more than 10 patients in total can be treated at any dose level unless \geq 3 of the 10 patients have achieved a PR or better

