4.1 Procedures by Study Day – Every 3-Week (Q3W) Dosing Schedule

The following procedures will be performed during the study. Regardless of dosing schedule, all patients will complete the same Screening procedures described in Section 4.1.1, as well as the same procedures described for End of Treatment (EOT; Section 4.1.8), 12-Week Follow-up Visit (Section 4.1.9) and Long-term Follow-up (Section 4.1.10).

Visit procedures described in Sections 4.1.2 - 4.1.7 are for patients on the Q3W dosing schedule.

The Schedule of Events for the Q3W and QW dosing schedules are shown in Table 5 and Table 7, respectively, in Appendix 12.1.

For QW dosing, most assessments remain uniform, with the following exceptions:

- Study Drug Administration occurs at Days 1, 8, and 15.
- Note: Bone Marrow Aspirate (BMA) or Biopsy for QW patients is still performed within 6 days prior to the first dose of the next cycle.
- Pharmacokinetic and Pharmacodynamics, ADA, WBC population, and additional renal function studies sampling schedule is adjusted according to the prescribed dosing schedule.

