5.9.1 Prohibited During Study

- Other anti-cancer therapy, with the exception of hormonal therapy for maintenance treatment of breast and prostate cancer.
- Hydroxyurea is not permitted after Cycle 1 unless approved by the Sponsor.
- Other investigational agents.
- Chronic treatment with corticosteroids (prednisone ≥12.5 mg/day or dexamethasone ≥2 mg/day, excluding inhaled steroids).
- Live vaccines.

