- 19. 12-lead ECG: On Day 1 of Cycle 3 and subsequent cycles, a 12-lead ECG is to be performed before the start of ADCT-402 infusion.
- 20. Concomitant medications to include prescription or over-the-counter medication, herbal or naturopathic products within the 14 days prior to the Cycle 1, Day 1 visit, during the study and 30 days following the patient's last dose of ADCT-402.
- 21. Premedication to be performed if a CTCAE Grade 2 or higher infusion-related hypersensitivity reaction is observed in 1 patient at any time during Part 1 of the study. All subsequent patients must receive prophylactic treatment on Day 1 of each cycle thereafter to reduce the risk of hypersensitivity reaction (Section 5.2).
- 22. ADCT-402: Patients will receive a 1-hour IV infusion of ADCT-402, at escalating doses, each 3-week (21-day) cycle. If ADCT-402 is well tolerated after the first infusion, the infusion duration may be shortened to 30 minutes for subsequent infusions for that patient, at the Investigator's discretion. Variations in infusion times due to minor differences in IV bag overfill/underfill and the institution's procedure for flushing chemotherapy lines will not result in protocol deviation. The IP window is +15 minutes.
- 23. For all patients, collection of AEs and SAEs will continue for up to 12 weeks (84 days) after the last dose of study drug or initiation of new anti-cancer treatment. Any SAEs that occur more than 84 days after the last dose of study drug do not need to be reported unless the Investigator considers the event to be related to study drug.
- 24. After documentation of disease progression or start of new anti-cancer treatment, patients will be contacted by telephone approximately every 12 weeks for up to 12 months after the last dose of study drug to collect survival information.
- 25. Information on anti-cancer treatment initiated after discontinuation of ADCT-402 to be recorded in the eCRF.

Date of Protocol: 19 April 2017 Page 77 Page 77

Table 7. Schedule of Study Procedures: Weekly (QW) Dosing

Procedure	Screen			Cycle 1					Cycle 2				Cycles 3 ntil PD/D		EOT 30 (+7)	12 Week Follow-	Follow- Up
rrocedure	Scr	D1 ±3d	D2 ¹	D3& ²	D8	D15	D1 ±3d	D2 ¹	D3&5 ²	D8 ±2d	D15 ±2d	D1 ±3d	D8 ±2d	D15 ±2d	days ³	Up Visit (± 1) week ⁴	12 (± 1) week
Informed consent	X																
Demography	X																
Medical history ⁵	X																
Serum or urine β-HCG pregnancy test	X	X ⁶													X		
Physical examination ⁷	X	X			X	X	X			X	X	X			X		

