- 13. Hematology: CBC to include WBC with a 5-part differential, platelet count, hemoglobin, hematocrit, and ANC. Peripheral blasts will be included in the hematology analysis for Part 2 only. If WBC is < 400 x 106/L differential is not required.
- 14. Samples for hematology, coagulation panel, biochemistry, and urinalysis will be collected prior to dosing unless the last sample was collected: <24 hours before the start of ADCT-402 infusion on Day 1 of Cycle 1, or <72 hours before the start of ADCT-402 infusion on Day 1 of Cycle 2 and subsequent cycles.
- 15. Coagulation panel: PTT and INR; PT expressed in seconds is optional.
- 16. Biochemistry: Alanine aminotransferase, aspartate aminotransferase, gamma-glutamyl transferase, alkaline phosphatase, amylase, lipase, total bilirubin, sodium, potassium, calcium, magnesium, blood urea nitrogen or urea, carbon dioxide/bicarbonate, chloride, creatinine, creatine phosphokinase, total protein,

- albumin, glucose, triglycerides, total cholesterol, phosphorus, and lactate dehydrogenase. At Days 1, 8 and 15 of each cycle, biochemistry will include creatinine clearance (calculated using the Cockcroft and Gault formula [Cockcroft and Gault, 1976]).
- 17. Urinalysis to include: pH, specific gravity, protein, glucose, ketones, nitrites, occult blood and bilirubin. The urinalysis may be performed using a urine dipstick.
- 18. 12-lead ECG: On Days 1 and 2 of Cycles 1 and 2, a 12-lead ECG is to be performed before the start of the ADCT-402 infusion, within 30 minutes of the end of infusion, and 3 hours (± 30 minutes) and 24 (± 2.4) hours after the end of infusion.
- 19. 12-lead ECG: On Day 1 of Cycle 3 and subsequent cycles, a 12-lead ECG is to be performed before the start of ADCT-402 infusion.
- 20. Concomitant medications to include prescription or over-the-counter medication, herbal or naturopathic products within the 14 days prior to the Cycle 1, Day 1 visit, during the study, and 30 days following the patient's last dose of ADCT-402.
- 21. Premedication to be performed if a CTCAE Grade 2 or higher infusion-related hypersensitivity reaction is observed in 1 patient at any time during Part 1 of the study. All subsequent patients must receive prophylactic treatment on Days 1, 8 and 15 of each cycle thereafter to reduce the risk of hypersensitivity reaction (Section 5.2).

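### Protocol Section 5.2 limits its mandatory hypersensitivity prophylaxis to Day 1 of each cycle, while Table 7 requires it on Days 1, 8 and 15 for weekly dosing and cites Section 5.2 for the regimen

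*Protocol*

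**What the plan says.** Protocol Section 5.2 sets the trigger (one Grade 2 or higher infusion-related hypersensitivity reaction at any time in Part 1) and then makes prophylaxis compulsory for every later patient, "as described below or as per the institution's standard of care". The listed regimen has four items:

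- oral dexamethasone 20 mg at 12 and at 6 hours before the infusion;
- IV diphenhydramine 50 mg at 30 minutes before;
- IV ranitidine 50 mg at 30 minutes before;
- a short oral dexamethasone course afterwards.

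The three pre-infusion items share the same opening, as in "On Day 1 of each cycle, patients will be given 50 mg of ranitidine (or equivalent) IV". The last item reads "For 2 days following administration of ADCT-402 on Day 1, all patients are to take dexamethasone 4 mg orally, twice per day".

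The schedules differ by regimen. Table 5 (Q3W), footnote 21: "All subsequent patients must receive prophylactic treatment on Day 1 of each cycle thereafter". Table 7 (QW), footnote 21: "All subsequent patients must receive prophylactic treatment on Days 1, 8 and 15 of each cycle thereafter". Both footnotes cite Section 5.2. The premedication row of Table 7 is marked on Days 1, 8 and 15 in Cycle 1, Cycle 2 and Cycles 3 onward.

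Section 4.1 points sites to the schedule for their regimen: "The Schedule of Events for the Q3W and QW dosing schedules are shown in Table 5 and Table 7, respectively". Section 3.2 makes the QW schedule conditional: "Weekly dosing will be implemented at the discretion of the DESC".

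**The concern.** Section 5.2 is the only place that gives drugs, doses and times for the mandatory prophylaxis, and Table 7 refers the reader there. For Q3W the two agree. For QW, the table requires cover on three days and the regimen it cites provides for one. A site that works from the regimen text, which is the natural source when writing premedication orders, would give the Day 8 and Day 15 infusions without the listed pre-infusion drugs.

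What is at stake is patient safety. The prophylaxis exists to lower the risk of hypersensitivity reactions and comes into force only after such a reaction has been seen. In Cycle 1, Days 8 and 15 also fall inside the one-cycle DLT observation period. A Grade 3 or higher hypersensitivity reaction on those days is a DLT (Section 6.3.1) and ends treatment for that patient (Section 4.2.1).

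**Working it through.** The plan states no statistical figure on this point, so the check compares the texts and adds one hand sum.

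**Texts side by side**

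| Source | Regimen | Days of prophylaxis |
|---|---|---|
| Section 5.2, three pre-infusion items | not specified | Day 1 |
| Section 5.2, post-infusion dexamethasone | not specified | after the Day 1 administration |
| Table 5, footnote 21 | Q3W | Day 1 |
| Table 7, premedication row and footnote 21 | QW | Days 1, 8 and 15 |

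**Does any other text repair Section 5.2?**

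- Section 4.1 lists how QW procedures differ from Q3W. Premedication is not on that list.
- Section 4.1.2 says Day 1 is the infusion day, but Section 4.1 restricts Sections 4.1.2 to 4.1.7 to Q3W patients.
- Section 5.9.2 describes a dexamethasone regimen, one part of it limited to Week 1/Day 1 whatever the schedule. That is a separate prophylactic course the DESC may institute on emerging safety and PK data. It says nothing about when the Section 5.2 regimen is given.

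**Infusions outside the Section 5.2 wording.** QW infusions per cycle: 3. Covered by the Day 1 wording: 1. Not covered: 3 − 1 = 2 (Days 8 and 15).

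**Dexamethasone per QW cycle under Table 7.** Inputs from Section 5.2:

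- Pre-infusion, per infusion: 2 × 20 mg = 40 mg.
- Post-infusion, per course: 2 days × 2 doses × 4 mg = 16 mg.

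Table 7 requires the pre-infusion drugs on all three days. Only the post-infusion course remains open:

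- after Day 1 only: 3 × 40 + 16 = 136 mg;
- after every infusion: 3 × (40 + 16) = 168 mg;
- difference: 168 − 136 = 32 mg, which is two extra courses (2 × 16), or 32/136 = about 24%.

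**The case against.** The strongest reply is that the documents already resolve the conflict. Section 4.1 sends QW sites to Table 7, the opening of Section 6 sends study procedures to Section 4.1 and the Appendix 12.1 tables, and the Table 7 footnote is worded as an obligation. A schedule-specific instruction should prevail over a general one, and giving the pre-infusion drugs before each infusion breaches neither text. Section 5.2 also accepts institutional standard of care as a full alternative. It requires drugs for severe reactions to be at hand, and it gives 48 hours of oral ranitidine and diphenhydramine after the infusion to any patient with a Grade 1 or 2 reaction, without a Day 1 limit.

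Much of this stands. It shows what was intended for QW and makes the point minor. It does not make Section 5.2 correct: the section that Table 7 cites still states the wrong days for QW. The 48-hour treatment follows a reaction; it is not prophylaxis.

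On the post-infusion course, one can argue that the literal anchor to Day 1 settles it. That is the plainer reading. But footnote 21 cites Section 5.2 as a whole, so a reading that repeats the full regimen is also possible. One sentence would close the question.

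Two stronger readings are tempting:

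- *QW steroid exposure could vary threefold, from 56 mg (40 + 16, Day 1 only) to 168 mg.* This is not supported. Table 7 already requires pre-infusion cover on all three days, so 56 mg is not a compliant QW total under the listed regimen. The live contrast is 136 against 168 mg.
- *The prophylaxis collides with the steroid prohibition in Section 5.9.1,* which bars "Chronic treatment with corticosteroids (prednisone ≥12.5 mg/day or dexamethasone ≥2 mg/day, excluding inhaled steroids". This is not supported either. The prohibition is on chronic treatment, and Section 5.9.2 lists this prophylaxis as mandatory under permitted treatments. Averaging intermittent doses over a cycle to compare them with 2 mg/day is a construction the protocol does not use.

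**Conclusion.** The inconsistency is real and specific to QW: as worded, Section 5.2 leaves 2 of 3 infusions per cycle outside the listed pre-infusion prophylaxis that Table 7 requires. The post-infusion dexamethasone is a secondary gap worth 32 mg per QW cycle.

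It has practical effect only if three conditions hold together: a Grade 2 or higher infusion-related reaction occurs in Part 1, the DESC opens QW dosing, and the site uses the listed regimen rather than its own standard of care. The documents do not show whether the first two occurred. SAP Section 4.7.1 contains QW exposure formulas, but that does not prove QW patients were treated.

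The point is minor. No statistical figure changes. A reader might infer that the DLT assessment is compromised. The documents do not support that, because Section 6.3.1 counts Grade 3 or higher hypersensitivity as a DLT whether or not premedication was given. Missed prophylaxis might affect how often such reactions occur, but the documents give nothing from which to compute this. SAP Section 3.3 reports that the trial stopped before dose escalation was complete, which limits the practical effect further.

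**What to change.** Amend Section 5.2. In the three pre-infusion items (dexamethasone, diphenhydramine, ranitidine), replace the Day 1 opening with: *Before each ADCT-402 infusion (Day 1 for Q3W; Days 1, 8 and 15 for QW)*. This aligns the text with Tables 5 and 7 and adds no steroid beyond what Table 7 already requires.

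In the same amendment, have the sponsor and the DESC state whether the 2-day post-infusion dexamethasone follows Day 1 only or every infusion. That is a clinical decision, and the documents do not determine it. Choosing every infusion adds 32 mg of dexamethasone per QW cycle. Section 5.9.1 needs no change.

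The cost is a short protocol amendment with the usual approvals, since Section 10.2.1 requires an amendment for any change in the study plan. No new data are collected and the SAP does not change: SAP Section 4.6 already lists premedication separately.
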